### **7.3. Vital Signs**

Vital signs will be summarized for the on-treatment phase.

Descriptive statistics will be provided by treatment group for vital signs (systolic and diastolic blood pressure [mmHg], pulse [beats/min], respiration [breaths/min], and body temperature [°C]) as follows:

- Baseline value
- Values at each postbaseline time visit
- Change from Baseline at each postbaseline visit

A Baseline value will be defined as the last available value collected on or prior to the date/time of first dose of study drug. Change from Baseline to a postbaseline visit will be calculated for any postbaseline visit including follow-up visits.

In the case of multiple values in an analysis window, data will be selected for analysis as described in [Section 3.6.5](#).

A by-subject listing of vital signs will be provided by subject ID number and visit in chronological order.

### **7.4. Prior and Concomitant Medications**

Medications collected at screening and during the study will be coded using World Health Organization (WHO) Drug dictionary (WHODrug Global 1 Sep 2020).

#### **7.4.1. Prior Medications**

Prior medications are defined as any medications taken before a subject took the first study drug.

Prior medications will be summarized by Anatomical Therapeutic Chemical (ATC) drug class Level 2 and preferred name using the number and percentage of subjects for each treatment group and overall. A subject reporting the same medication more than once will be counted only once within each ATC drug class. The summary will be ordered alphabetically by ATC medical class and then by preferred term in order of descending overall frequency within each ATC medical class. For drugs with the same frequency, sorting will be done alphabetically.

A medication will be considered as a prior medication if it meets one the following criteria:

- A medication with a start date prior to the first dose date of study drug will be included in the prior medication summary regardless of when the stop date is.

- If a partial start date is entered, the medication will be considered prior unless the month and year (if day is missing) or year (if day and month are missing) of the start date are after the first dose date.
- A medication with a completely missing start date will be included in the prior medication summary, unless otherwise specified.

Summaries will be based on the Safety Analysis Set.

#### **7.4.2. Concomitant Medications**

Concomitant medications are defined as medications taken while a subject took study drug. Use of concomitant medications will be summarized by ATC drug class Level 2 and preferred name using the number and percentage of subjects for each treatment group. A subject reporting the same medication more than once within each ATC drug class will be counted only once when calculating the number and percentage of subjects who received that medication. Medications may appear under multiple ATC drug classes. The summary will be ordered alphabetically by ATC medical class and then by preferred term in descending overall frequency within each ATC medical class. For drugs with the same frequency, sorting will be done alphabetically.

A medication will be considered as a concomitant medication if it meets one the following criteria:

- A medication with a start date prior to or on the first dose date of study drug, and continued to be taken after the first dose date.
- A medication started after the first dose date
- If a partial start date is entered, any medication with the month and year (if day is missing) or year (if day and month are missing) before the study drug stop date and the stop date after the first dose date of study drug. If a partial stop date is entered, any medication with the month and year (if day is missing) or year (if day and month are missing) after the date of first study drug
- A medications started and stopped on the same day as the first dose
- Medications with completely missing start and stop dates, unless otherwise specified.

A medications with a stop date prior to the date of first dose date of study drug will be excluded from the summary.

Summaries of prior and concomitant medications and HBV concomitant medications will be based on the Safety Analysis Set.

All the prior and concomitant medications will be provided in a by-subject listing sorted by subject ID number and administration date in chronological order.

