## **6.3 Concomitant Medications**

A concomitant medication is defined as any prescription or over-the-counter preparation, including vitamins, medications, vaccinations, herbal preparations and supplements that is taken by a subject during the conduct of the clinical trial.

All concomitant medications taken from the date the informed consent is signed through end of study or “lost to follow-up” must be recorded in the subject’s source documentation. This information should include the name of the medication, the dosage, the start and stop dates, and the indication for which the concomitant medication was administered.

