### **3.6. Analytic Definitions**

#### **3.6.1. Definition of Study Drug**

In this study, study drug is defined as VBR and AB-729.

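### SAP 7.4.2 limits concomitant medications to time on study drug, but one counting criterion has no end date, so medications first started off treatment enter the table

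*Combined protocol and SAP*

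**What the plan says.** SAP 7.4.2 opens with a definition: "Concomitant medications are defined as medications taken while a subject took study drug". SAP 3.6.1 fixes the term: "In this study, study drug is defined as VBR and AB-729". NrtI is therefore not study drug.

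The section then lists criteria under the sentence "A medication will be considered as a concomitant medication if it meets one the following criteria", so any one of them is enough. The second reads, in full, "A medication started after the first dose date". The criterion for partial start dates is narrower. It asks for a month and year, or a year alone, "before the study drug stop date and the stop date after the first dose date of study drug". The only stated exclusion is at the front end: "A medications with a stop date prior to the date of first dose date of study drug will be excluded from the summary".

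Protocol 6.3 uses a wider concept, a preparation "that is taken by a subject during the conduct of the clinical trial", and sets the recording period accordingly: "All concomitant medications taken from the date the informed consent is signed through end of study" or loss to follow-up.

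**The concern.** The definition and the counting rule in the same section give different answers for any medication first started after VBR and AB-729 have ended. A programmer working from the definition would leave it out. One working from the criteria would put it in. The second result carries a label, concomitant with study drug, that the SAP's own definition denies it.

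Concomitant medication use is one of the safety analyses named in protocol 10.4.5, and its usual purpose is to help interpret adverse events and possible interactions. For example, protocol 6.3.1 prohibits the Table 8 medications only until 2 weeks after the last VBR dose. One of them started later in follow-up breaks no rule, yet it would appear in the table as if taken together with study drug. A reader of the report could take that for an interaction exposure or a deviation that did not occur.

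**Working it through.** No sample size, power or error rate is involved, and the plan states no figure to reproduce. The check is to run typical records through each rule, after fixing the time limits.

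**Time limits**

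1. As designed (protocol synopsis), treatment lasts 48 weeks and follow-up 48 weeks, so the window after treatment is up to 96 − 48 = 48 weeks.
2. SAP 3.6.3 ends the On-Treatment Phase at the later of last VBR dose + 1 day and last AB-729 dose + 56 days. The last AB-729 dose is at Week 40 (protocol 8.3.3), and 56 days is 8 weeks, so for a Group 3 completer the phase ends at Week 40 + 8 = Week 48. In Groups 1 and 2 it runs slightly past Week 48, because VBR continues until the Week 48 laboratory results are available.
3. Follow-up visits review concomitant medications (protocol Tables 10 and 11), so starts after these dates can be in the database.

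**Records against rules**

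| Record | SAP 7.4.2 definition | SAP 7.4.2 criteria | Protocol 6.3 |
|---|---|---|---|
| New drug, complete start date, On-Treatment Phase | In | In | In |
| New drug, complete start date, Off-Treatment or NrtI-Restart Phase | Out | In, by the second criterion | In |
| Same drug, only month and year of start known, both after the study drug stop date | Out | Out by the partial-start criterion; arguably in by the second | In |
| Baseline NrtI, stopped and restarted | In, from use during treatment | In, by the first criterion; restart adds nothing | In |
| Restart on a different NrtI, complete date | New agent out | New agent in | In |

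The second row is the contradiction. The stop-date exclusion does not reach it, because such a drug cannot have stopped before the first dose. No other section supplies an end date.

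The third row is less clear-cut. The second criterion does not say that it is limited to complete dates, and a separate sentence on partial stop dates could also admit some of these records. The safe statement is that one criterion carries a stop-date limit, the other carries none, and the SAP does not say which governs.

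For the fourth row, protocol 5.2 requires every subject to enter on a stable NrtI. If that NrtI is held as a medication record, it began before the first dose and continued, so it already counts. SAP 7.4.2 counts a subject once for repeated use of the same medication within an ATC class.

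**A side point on the partial-date limit.** SAP 3.6.4 defines the last dose date of study drug as the later of the two drugs' last doses. If the study drug stop date means this, it falls at Week 40 in Group 3, 8 weeks before the On-Treatment Phase ends there. The two limits need to be made the same.

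**Phase split.** SAP 7.1.6, 7.2.1.2 and 7.2.2 build TEAE, laboratory abnormality and direct bilirubin tables separately for the three phases, and SAP 7.3 restricts vital signs summaries to the On-Treatment Phase. SAP 7.4.2 does neither.

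**The case against.** The strongest reply is that the criterion is right and the definition is the outlier. Protocol 6.3 counts anything taken during the trial, and TEAEs also run to the end of the study (protocol 10.4.5.1, SAP 7.1.5.1), so an open-ended criterion agrees with both. That is true, and it is why changing the definition is as valid a repair as bounding the criterion. It does not remove the inconsistency, because the SAP still says something narrower. The comparison with TEAEs is also incomplete: those tables are split by phase, so an off-treatment event is shown as such, while an off-treatment medication is not.

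The second reply is that little depends on it. The table is descriptive, it supports a Synoptic CSR, and it is not part of the primary endpoint. A by-subject listing in order of administration date is planned, from which late starts can be picked out. The study was terminated in February 2023, before SAP version 1.0 (17 May 2023), so full follow-up was no longer in prospect. Subjects reaching Week 48 after the announcement were to leave at the next follow-up visit. All of this stands and limits the importance of the point. The listing lets a careful reader recover the information but does not correct the table.

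**Conclusion.** The point holds as an internal contradiction of minor weight. As written, SAP 7.4.2 tabulates medications newly started in the Off-Treatment or NrtI-Restart Phase as concomitant with study drug, against its own definition. This assumes that the programmer follows the listed criteria and that at least one subject started a new medication after the On-Treatment Phase. The documents give no rate of such starts, so the number of subjects affected cannot be stated.

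Two stronger readings are tempting, and the documents support neither.

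- **Restarted NrtI distorts the comparison between arms.** A reader might infer this because stopping NrtI requires HBsAg below 100 IU/mL, so restarts could gather in the AB-729 groups. Restarting the same NrtI changes no count, for the reasons in the fourth row of the table. Only a switch to a different NrtI could add an entry, and nothing in the documents says how often that would happen. Protocol 6.2.2 also sends NrtI dosing to the subject diary, so a medication record for the restart is itself an assumption.
- **About half of the table is wrong.** The designed schedule gives 48/96 = 50% of time after treatment. At a constant start rate that would be a share of new medication starts, whereas the table reports subjects, once per medication. Drugs carried over from before the first dose, and drugs already used on treatment, dilute any effect. The 48 weeks of follow-up had also been cut short by the time the SAP was written.

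**What to change.** Choose one definition and make every criterion follow it. Either option works:

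1. **Keep the SAP definition.** Restrict the second criterion to medications started after the first dose date and no later than the last day of the On-Treatment Phase as defined in SAP 3.6.3. Replace the study drug stop date in the partial-start criterion by the same day, and state which criterion governs partial dates. Tabulate medications first started in the Off-Treatment and NrtI-Restart Phases separately.
2. **Adopt the protocol 6.3 definition.** Replace the opening sentence of SAP 7.4.2 accordingly and present the table by On-Treatment, Off-Treatment and NrtI-Restart Phase, as SAP 7.1.6 and 7.2.1.2 already do for TEAEs and laboratory abnormalities.

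Neither needs new data, since start dates and phase boundaries are already required elsewhere. The cost is a short wording change, one additional or split table, and a little programming. SAP section 1 provides for changes after finalization to be documented in the Synoptic CSR, so the correction can be recorded there if the SAP is closed.

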## **7.5. Electrocardiogram Results**

A shift table of the investigators' assessment of ECG results at each visit compared with baseline values will be presented by treatment group using the following categories:

- normal
- abnormal (not clinically significant)
- abnormal (clinically significant)
- missing/not done

The number and percentage of subjects in each cross-classification group of the shift table will be presented. Subjects with a missing value at baseline or postbaseline will not be included in the denominator for percentage calculation.

A by-subject listing for ECG assessment results will be provided by subject ID number and visit in chronological order.

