### **8.8.3 Electrocardiograms**

A standard 12-lead ECG will be obtained as specified in the Schedule of Assessments ([Table 9](#), [Table 10](#), [Table 11](#)). Prior to the conduct of 12-lead ECGs, subjects should rest in a supine position for 10 minutes. Electrocardiograms should be conducted in accordance with local practice and equipment. The ECG assessment will include interpretation of the tracings (eg, rhythm, presence of arrhythmia or conduction defects, morphology, any evidence of myocardial infarction, or ST segment, T-wave, and Uwave abnormalities). The Investigator or a physician subinvestigator is responsible for reviewing and overreading the ECG interpretation, for assessing whether the ECG machine interpretation findings are accurate, appropriate, normal or abnormal, and for providing corrected interpretations as appropriate. In addition, any abnormal ECGs will be assessed for clinical significance.

Additional ECGs may be obtained if clinically indicated and will be obtained if abnormal and clinically significant or thought to be an error (eg, lead placement error, movement artifact, etc.). Any additional relevant data obtained by the Investigator during the course of this study will be recorded in the subject's source documentation. The Investigator or a physician subinvestigator will review all ECGs, evaluate the results, and sign/date the tracing or report. For any ECG abnormality that the Investigator considers clinically significant, the Investigator will:

- Repeat the ECG;
- Obtain follow-up ECG(s) if any significant abnormalities are detected after study drug administration to document resolution and as clinically indicated;
- Record as an AE any ECG abnormality that: (1) is confirmed and the Investigator considers clinically significant; (2) requires a subject to be discontinued from the study; or (3) the abnormality requires a subject to receive treatment ([Section 8](#)).

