**Table 3-2 On-Treatment Analysis Visit Windows for HBV DNA, HBcrAg, and ECG**

Nominal Visit	On-Treatment Phase Nominal Study Day	Visit Window Study Day	
		Lower Limit	Upper Limit
Baseline	1	(none)	1
Week 12	84	2	126
Week 24	168	127	210
Week 36	252	211	294
Week 48	336	295	≥336

The analysis windows for the Off-Treatment Phase assessments for subjects meeting Treatment Stopping Criteria of HBV DNA, HBV TNA, HBV RNA, HBsAg, Vital signs, Chemistry, Hematology, Coagulation, and Urinalysis are provided in [Table 3-3](#).

**Table 3-3 Off-Treatment Phase Analysis Visit Windows for HBV DNA, HBV TNA, HBV RNA, HBsAg, Vital Signs, Chemistry, Hematology, Coagulation, and Urinalysis for Subjects Meeting Treatment Stopping Criteria**

Nominal Visit	Off-Treatment Phase Nominal Study Day	Visit Window Study Day	
		Lower Limit	Upper Limit
Off-Treatment Day 1	1	(none)	1
Off-Treatment Week 4	28	2	42
Off-Treatment Week 8	56	43	70
Off-Treatment Week 12	84	71	98
Off-Treatment Week 16	112	99	126
Off-Treatment Week 20	140	127	154
Off-Treatment Week 24	168	155	182
Off-Treatment Week 28	196	183	210
Off-Treatment Week 32	224	211	238
Off-Treatment Week 36	252	239	266

Nominal Visit	Off-Treatment Phase Nominal Study Day	Visit Window Study Day	
		Lower Limit	Upper Limit
Off-Treatment Week 40	280	267	294
Off-Treatment Week 44	308	295	322
Off-Treatment Week 48	336	323	≥ 336

The analysis windows for the Off-Treatment Phase assessments of HBcrAg and HBeAg for subjects meeting Treatment Stopping Criteria are provided in [Table 3-4](#).

Table 3-4 **Off-Treatment Phase Analysis Visit Windows for HBcrAg and HBeAg for Subjects Meeting Treatment Stopping Criteria**

Nominal Visit	Off-Treatment Phase Nominal Study Day	Visit Window Study Day	
		Lower Limit	Upper Limit
Off-Treatment Day 1	1	(none)	1
Off-Treatment Week 12	84	2	126
Off-Treatment Week 24	168	127	210
Off-Treatment Week 36	252	211	294
Off-Treatment Week 48	336	295	≥ 336

The analysis windows for Off-Treatment Phase assessments for subjects meeting Treatment Stopping Criteria of ECG are provided in [Table 3-5](#).

Off-Treatment Phase Analysis Visit Windows for HBcrAg and HBeAg for Subjects Meeting Treatment Stopping Criteria

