**3.6.6. Selection of Data in the Event of Multiple Records in an Analysis Visit Window**

Depending on the statistical analysis method, single values may be required for each analysis window. If a single value is needed, but multiple valid, nonmissing measurements exist in an analysis window, records will be chosen based on the following rules:

- For baseline, the last nonmissing value on or prior to the first dose date of study drug will be selected, unless specified differently. If there are multiple records with the same time or no time recorded on the same day, the record with the lowest accession number will be used.
- For postbaseline values:
  - The record closest to the nominal day for that visit will be selected.
  - If there are 2 records that are equidistant from the nominal day, the later record will be selected.
  - If there is more than 1 record on the selected day with the same time, the retest record will be selected. If there is no clear indication for which record is the retest record, then the record with the lowest accession number will be used.

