#### **7.2.1.2. Summaries of Laboratory Abnormalities**

A summary (number and percentage of subjects) for treatment-emergent laboratory abnormalities will be provided by lab test and treatment group; subjects will be categorized according to the most severe postbaseline abnormality grade for a given laboratory test.

Treatment-emergent lab abnormalities will be summarized based on the Safety Analysis Set. Tables will be created per study phase (i.e. On-Treatment Phase, Off-Treatment Phase, and NrtI-Restart Phase).

For all summaries of laboratory abnormalities, the denominator is the number of subjects with nonmissing postbaseline values in each phase.

The maximum post-baseline grade in each phase will be tabulated for each laboratory test, and percentages will be based on the number of subjects with a post-baseline evaluation of the specific laboratory test. The laboratory abnormalities during the follow-up period will also be summarized.

A by-subject listing of graded laboratory abnormalities will be provided by subject ID number and visit in chronological order. This listing will include all test results that were collected throughout the study for the lab test of interest, with all applicable severity grades displayed.

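### The by-visit ECG shift table keeps one tracing per wide window, so unscheduled, repeat and termination ECGs can fall out of the by-arm summary; add a worst-postbaseline shift per phase

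*Combined protocol and SAP*

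**What the plan says.** SAP 7.5 plans one ECG summary, a shift table of the investigator's assessment: "ECG results at each visit compared with baseline values will be presented by treatment group using the following categories". The categories are normal, abnormal but not clinically significant, abnormal and clinically significant, and missing. A by-subject listing accompanies it. No worst-value or any-time row is planned.

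The on-treatment windows are in SAP Table 3-2, titled "On-Treatment Analysis Visit Windows for HBV DNA, HBcrAg, and ECG". Off-treatment and NrtI-restart ECG windows are in Tables 3-5 and 3-8. SAP 3.6.6 governs several records in one window. It applies "If a single value is needed, but multiple valid, nonmissing measurements exist in an analysis window", and for postbaseline data the rule is "The record closest to the nominal day for that visit will be selected". On ties, "If there are 2 records that are equidistant from the nominal day, the later record will be selected". Nothing in the rule prefers the worse or the unscheduled record.

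Protocol 8.8.3 expects ECGs beyond the schedule: "Additional ECGs may be obtained if clinically indicated and will be obtained if abnormal and clinically significant". It also asks for repeat and follow-up tracings after significant findings. Protocol 8.5 includes an ECG at the Premature Termination visit.

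Laboratory data are handled differently in SAP 7.2.1.2: "The maximum post-baseline grade in each phase will be tabulated for each laboratory test".

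**The concern.** A nearest-to-nominal rule suits a trajectory of scheduled measurements. For a categorical safety reading it favors the routine tracing over the one taken because something was suspected. A clinically significant ECG that has resolved by the scheduled visit leaves no mark in the by-arm table.

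The rule can also err the other way, keeping an abnormal scheduled tracing when a later repeat is normal. The planned table therefore does not show how many subjects in each arm ever had a clinically significant ECG. Protocol 10.4.5.3 allows ECGs to be summarized by incidence of abnormalities, and a by-visit shift cannot supply per-subject incidence.

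**Working it through.** **1. Window lengths** (upper minus lower plus 1, Table 3-2)
- Week 12, Days 2 to 126: 126 − 2 + 1 = 125 days.
- Week 24, Days 127 to 210: 210 − 127 + 1 = 84 days.
- Week 36, Days 211 to 294: 294 − 211 + 1 = 84 days.
- Week 48: from Day 295, no upper limit.
- Off-treatment and restart Week 12 (Tables 3-5 and 3-8), Days 2 to 210: 210 − 2 + 1 = 209 days. Week 48 there is open-ended from Day 211.

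The SAP's upper limits reproduce as midpoints between nominal days: (84 + 168)/2 = 126, (168 + 252)/2 = 210, (252 + 336)/2 = 294; off treatment, (84 + 336)/2 = 210.

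**2. Which days lose.** Scheduled on-treatment ECGs have a ±3-day visit window, which is 7 days. If the scheduled ECG falls inside it, an additional ECG outside it is never selected:
- Week 12: (125 − 7)/125 = 118/125 = 94% of days.
- Weeks 24 and 36: (84 − 7)/84 = 77/84 = 92% of days.

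These are shares of calendar days. They are not shares of ECGs or subjects.

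**3. Both directions of error**
- Clinically significant ECG on Day 28, scheduled ECG on Day 84. Distances from nominal Day 84 are 56 and 0, so the Day 84 tracing is used and the finding is missed.
- Abnormal scheduled ECG on Day 85, normal repeat on Day 90. Distances are 1 and 6, so the unconfirmed abnormal tracing stays.
- Abnormal scheduled ECG on Day 81, normal repeat on Day 84. Distances are 3 and 0, so the repeat is used. The outcome depends on which side of nominal the visit fell.

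**4. Termination ECGs by arm.** SAP 1.2 says that subjects reaching Week 48 after the February 2023 announcement were to have the Premature Termination visit at the next follow-up visit and stop VBR then. Take that visit as Week 52, nominal Day 364.
- *Groups 1 and 2.* SAP 3.6.3 runs the On-Treatment Phase to the last VBR dose plus 1 day, so the ECG is on treatment. Table 3-1 has Week 52 and Week 56 windows, but Table 3-2 has none for ECG. The tracing goes into Week 48 at distance 364 − 336 = 28, and loses to a Week 48 ECG done within ±3 days.
- *Group 3.* The last AB-729 dose is at Week 40 (Day 280), and 280 + 56 = 336. The Day 364 ECG is Off-Treatment, on off-treatment day 364 − 336 + 1 = 29. It falls in the Off-Treatment Week 12 window, which is Days 2 to 210 in both Table 3-5 and Table 3-8, and can be counted.

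This is inferred from the phase and window rules. The number of subjects concerned is not given.

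**5. Effect of one subject** at planned arm sizes: 1/15 = 6.7 percentage points in Group 2 or 3, and 1/30 = 3.3 in Group 1.

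**The case against.** The strongest reply is that the finding is not lost. Protocol 8.8.3 requires an adverse event for a confirmed clinically significant ECG abnormality, and for one that needs treatment or takes the subject off the study. SAP 7.1.6 tabulates treatment-emergent events by arm and phase, and SAP 7.5 lists ECG results by subject. This stands. It leaves the ECG summary itself incomplete, together with abnormalities that meet none of the adverse-event conditions and so have no by-arm count.

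A reader might infer that the rule weakens the primary analysis or hides a cardiac signal. The documents do not support that. The primary endpoint covers adverse events, discontinuation due to them and abnormal laboratory results; ECG is not named. Nor would a difference between the shift table and the adverse-event tables be a contradiction, since one shows status at a visit and the other incidence over a phase.

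A reader might also infer that every indicated ECG is dropped. It is passed over only when another ECG in the window is nearer the nominal day. It is used when the scheduled one is missing or further away, as can happen when a subject stops early. For repeats on the same day and time, SAP 3.6.6 already selects the retest.

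Three further points stand. SAP 7.5 does not cite 3.6.6, so its use is inferred from the ECG-specific windows and the form of the table. Neither Protocol 8.4 nor the unscheduled column of Table 9 includes an ECG, so indicated tracings may not reach the database. And the SAP is deliberately reduced for a Synoptic CSR; vital signs also have no worst-value row.

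**Conclusion.** The point holds for the by-arm ECG summary and no further. As planned, the table can miss transient clinically significant ECGs, can retain unconfirmed ones, and may treat termination ECGs differently in Groups 1 and 2 than in Group 3. The net direction is not established, so a claim of systematic undercounting would go too far.

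The size of the gap is unknown: the documents give no rate of additional ECGs or of ECG abnormalities. The 94% and 92% show how rarely an off-schedule day can win, not how often the table would be wrong. The conclusion assumes that SAP 3.6.6 is applied to the shift table and that scheduled ECGs are done within their visit windows. For indicated ECGs it also assumes that they are in the database; Premature Termination ECGs are a required assessment and do not depend on that. This is an inexpensive improvement to a descriptive safety summary.

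**What to change.** Add to SAP 7.5 a shift from Baseline to the worst postbaseline investigator assessment, by treatment group and study phase. Use every ECG in the database: scheduled, unscheduled, repeat and Premature Termination. Flag findings not confirmed on repeat. Keep the by-visit table. State in the SAP whether unscheduled ECGs are captured in the database; if they are not, footnote the table accordingly.

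The cost is one more table from ECGs already in the database, with the flag derivable only where repeats are recorded. The SAP allows changes after finalization to be documented in the Synoptic CSR. The downside is that subjects with more ECGs have more chances of an abnormal reading. In an open-label study the decision to take an extra tracing may differ by arm, and the flag deals with false positives but not with unequal testing. So also show the number of ECGs per subject by arm.
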